## 1. INTRODUCTION

This Statistical Analysis Plan (SAP) is based on the study Protocol Amendment 2 Final v3.0 dated October 26th, 2018.

This document provides additional details concerning the statistical analyses outlined in the protocol and reflects any changes to the protocol from any amendments. This plan will not repeat all the definitions given in the protocol but will provide further details of the summaries and analyses planned therein.

## 2. STUDY OBJECTIVES

The co-primary objectives are:

- To demonstrate the efficacy of PPC-06 with respect to Psoriasis Area and Severity Index (PASI) for the treatment of moderate-to-severe plaque psoriasis, as compared to placebo at 24 weeks.
- To demonstrate the efficacy of PPC-06 with respect to Investigator's Global Assessment (IGA) at 24 weeks.

The secondary objectives are:

- To assess the efficacy of PPC-06 as it relates to psoriasis-related symptoms and health-related quality of life (QoL) measures.
- To assess the safety and tolerability of PPC-06 in subjects with moderate-to-severe plaque psoriasis.
- To evaluate the pharmacodynamics (PD) of PPC-06 through immunological analysis of peripheral blood samples. The PD analysis will be covered in a separate report.

## 3. STUDY DESIGN

This is a randomized, double-blind, placebo-controlled, multicenter study designed to assess the safety and efficacy of PPC-06 (tepilamide fumarate) extended release [ER] tablets in subjects with moderate-to-severe plaque psoriasis. Study subjects will be enrolled at approximately 75 sites in the United States (US). The study will be comprised of 4 study periods: 1) Screening Period, 2) Double-Blind Titration Period 3) Double-Blind Treatment Period and 4) Post-treatment Follow-Up Period.

Following completion of the pre-randomization Screening Period (up to 4 weeks), approximately 400 eligible subjects will be randomly assigned in a 1:1:1:1 ratio to one of the 4 arms (PPC-06 400 mg QD, PPC-06 400 mg BID, PPC-06 600 mg BID, or placebo BID) and the subjects will enter the 5-week Double-Blind Titration Period. At Visit 3 (Week 4), the subjects will continue one

more week of titration dose (Week 5 of blister wallets) and will also be given a kit of bottles which will allow dosing until Visit 4 (Week 8).

Subjects will receive double-blind treatment from Week 6 through Week 24. Subjects will return to the clinic every 4 weeks ( $\pm 3$  days) thereafter, until Week 24, for drug accountability and to undergo safety and efficacy evaluations. Subjects will return at Week 25 for an End of Study (EOS) Safety Follow-Up Visit. There are nine expected visits total per subject.

Blood samples for pharmacodynamics (PD) assessments will be collected at Baseline and at Weeks 4, 8, 12, 16, 20, and 24. PD assessments will be conducted for all subjects, with the intent of evaluating psoriasis-associated inflammatory markers.

The Early Termination Visit (ETV) will be scheduled if the study drug is permanently discontinued for any reason (for example: due to meeting the protocol-mandated safety monitoring criteria or unresolved gastrointestinal [GI]-related intolerance).

The EOS Safety Follow-up Period will consist of 1 visit 1-week ( $\pm 3$  days) following the Week 24 Visit or the ETV. In the event that the Week 24 Visit or the ETV occurs  $> 1$  week following the last dose of the study drug, the EOS Safety Follow-up Visit may not be required. The ETV and/or EOS Safety Follow-Up Visit are not expected to be completed for subjects who withdraw full consent or are lost to follow up.

If necessary, the Investigator may decide to extend the follow-up visits beyond one week to monitor recovery of safety parameters (e.g., lymphopenia).

#### **4. HARDWARE AND SOFTWARE**

Statistical analysis will be performed following Novella standard operating procedures and on the Novella computer network. All statistical analysis will be performed using SAS Version 9.3 or higher with program code prepared specifically for the project by qualified Novella statisticians and SAS programmers.

#### **5. DATABASE CLOSURE**

After completion of all data review and cleaning procedures and approval by the sponsor, the clinical database will be closed, and the study will be unblinded. Any change to the clinical database after this time will require written authorization, with explanation, by the Sponsor and the Biostatistician. After final approval of analysis methodologies, population assignments, and database closure, the study will be unblinded.

#### **6. RANDOMIZATION**

IWRS will be used for randomization. The randomization scheme will be reviewed and approved by a member of the sponsor's Biostatistics and Data Management (BDM) group or designee. The sites will randomize eligible subjects by contacting IWRS at Visit 2 after all the relevant Baseline

procedures are completed and assessed as appropriate. A subject who fulfills the study eligibility requirements will be randomly assigned to treatment. The randomization will be stratified by prior biologic use.

The IWRS will assign a randomization number to the subject, which will be used to link the subject to the treatment group and will specify a unique Blister Wallet IP kit number for the IP to be dispensed to the subject at Visit 2 for the Titration Period. The sites will log in to IWRS during each subsequent subject visit to obtain the kit numbers of the Bottle Kits to be dispensed at study Visits 3-7.

## 7. SAMPLE SIZE DETERMINATION

It was determined that a sample size of 100 subjects per treatment group would detect a significant difference in proportion of PASI-75 and IGA responders from Baseline to Week 24 between each dose group of PPC-06 and placebo group, assuming a 15% response rate for the placebo group and 45% for PPC-06 at Week 24. To provide sufficient evidence of treatment effect, both PASI and IGA based response rate must reject at the same significance level. The hypothesis testing for the three dose groups will be conducted sequentially from high to low dose (600 mg BID, 400 mg BID and 400 mg QD); therefore, the 2-sided Type I error rate from a chi-squared test remains at the 0.05 level. Assuming 50% dropout rate, about 100 subjects per treatment arm will be randomized to get approximately 50 completers in each treatment arm. The total sample size of 400 subjects will yield at least 84% power for hypothesis testing of the co-primary endpoints of a difference in PASI-75 and IGA responders from Baseline to Week 24 between PPC-06 doses and placebo.

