7.3 Efficacy Assessments

Efficacy will be evaluated via psoriasis assessments and measures of QoL.

Psoriasis assessments include the PASI, the affected BSA, and the IGA. Subject-reported assessments of health-related QoL include the DLQI, 12-Item Short Form Survey (SF-12), the Quick Inventory of Depressive Symptomatology-Self Report (QIDS-SR), the WPAI:PSO, the HEOR, and the Pruritus NRS.

Other psoriasis assessments to be performed as applicable include the NAPSI for the target fingernail, the PSSI score, and the PP PGA score.

Brief descriptions of these assessments are presented as follows.

7.3.1 Co-Primary Efficacy Assessments: Psoriasis Area and Severity Index and Investigator's Global Assessment

The investigator or designee will assess the extent and severity of the subjects' psoriasis using the PASI scoring system and will perform a global assessment of disease severity using the IGA. The PASI scale is provided in [Appendix 1](#); the IGA is a 5-point scale which measures the investigator's or designee's impression of the disease at a single point. Assessments will be performed at the visits specified in [Table 1-1](#). Sites should make every effort to ensure consistency in evaluators across visits, especially between Baseline and Week 24.

Psoriasis Area and Severity Index

The PASI is a measure of the average redness, thickness, and scaliness of the lesions (each graded on a 0–4 scale) and weighted by the area of involvement ([Fredriksson, 1978](#)). There are a few validation studies performed describing, with some limitations, the construct validity, face validity, and sensitivity to change ([Ashcroft, 1999](#)). National Psoriasis Foundation Medical Advisory Board standardized the definitions of events of psoriasis recurrence based on PASI, including the definition of relapse, which is a loss of at least 50% of PASI improvement after discontinuation of treatment in patients who had achieved a clinically meaningful response; and rebound, which is PASI \geq 125% of Baseline or new generalized pustular, erythrodermic, or more inflammatory psoriasis ([Carey, 2006](#); [Gordon, 2005](#)). In the current trial, PASI improvement will be evaluated from Baseline to all visits during the Titration and Treatment Periods, and clinically meaningful response is defined as PASI-50 ([Carlin, 2004](#)).

Investigator's Global Assessment

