8.7.4 Control of Multiplicity

For the primary efficacy analysis (PASI-75 and IGA), each of the PPC-06 doses will be compared with placebo separately, sequentially from high to low dose to maintain the Type-I error rate. Therefore, no adjustments for multiplicity will be performed.

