## 12.8 Efficacy Analyses

### 12.8.1 Primary Efficacy Analyses

For each of the co-primary efficacy endpoints, proportion of subjects who achieved PASI-75 and IGA success at Week 24, will be tested to compare the difference between the subjects treated with PPC-06 and placebo, separately. To provide sufficient evidence of treatment effect, both PASI and

IGA based response rate must be rejected at the same significance level. The hypothesis testing for the three dose groups will be conducted sequentially from high to low dose; therefore, the 2-sided Type I error rate remains at the 0.05 level.

The primary efficacy analyses will be based on the FAS population using MI. Each multiple imputed dataset will be analyzed using a logistic regression model with treatment group, baseline BMI, and pooled analysis center as factors. The primary treatment comparisons will be the contrasts between the PPC-06 doses and placebo. The estimates and standard errors (SEs) of the log (odds ratio) based on the 50 imputed datasets will be combined by applying Rubin's rules for multiple imputed datasets. The combined log (odds ratio), odds ratio and associated 95% CI, and the resulting p-value will be provided. SAS Proc MI, Proc LOGISTIC, and Proc MIANALYZE will be utilized for these analyses. The averaged proportion of PASI-75 responders and IGA Success Rates over the 50 imputed datasets will also be presented.

Sensitivity analyses will be conducted using m-NRI and LOCF, following a same method as described above for each multiple imputed dataset. For each of the co-primary efficacy endpoints, proportion of subjects who achieved PASI-75 and IGA success at Week 24, will be tested to compare the difference between the subjects treated with PPC-06 and placebo, separately. PASI-75 and IGA Success Rates will be analyzed using a logistic regression model with treatment group, baseline BMI, and pooled analysis center as factors. The odds ratio between each PPC-06 group and placebo, along with the 95% CI and p-value will be reported.

Supporting analysis of the primary endpoints will also be performed using m-NRI based on the PP population.

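### The stated power of at least 84% is for one dose against placebo and leaves out the plan's own fixed dose sequence; at 50 completers per arm the two lower doses generally fall short of it

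*SAP*

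**What the plan says.** The sample size paragraph in SAP section 7, repeated almost unchanged in Protocol section 8.2, sets these inputs:

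- Response rates: "assuming a 15% response rate for the placebo group and 45% for PPC-06 at Week 24".
- Completers: "about 100 subjects per treatment arm will be randomized to get approximately 50 completers in each treatment arm", from an assumed 50% dropout.
- Test: chi-squared at two-sided 0.05, with both PASI-75 and IGA required to reject.
- Order: testing is "conducted sequentially from high to low dose (600 mg BID, 400 mg BID and 400 mg QD").

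It then gives a single power figure: "The total sample size of 400 subjects will yield at least 84% power for hypothesis testing of the co-primary endpoints of a difference", between PPC-06 doses and placebo.

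The sequence is the only control of multiplicity across doses. Protocol section 8.7.4 has the doses tested "sequentially from high to low dose to maintain the Type-I error rate. Therefore, no adjustments for multiplicity will be performed". SAP section 12.8.1 repeats the rule: "The hypothesis testing for the three dose groups will be conducted sequentially from high to low dose". Neither document gives power by dose, power under the sequence, or a correlation between the two endpoints.

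**The concern.** The plan uses the sequence to keep alpha at 0.05 but does not count what the sequence costs in power. Under a fixed sequence, the chance of a confirmatory claim for 400 mg BID is the chance that 600 mg BID and 400 mg BID both succeed on both endpoints. For 400 mg QD all three doses must succeed.

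The 84% sits straight after the gatekeeping rule, carries no label and refers to the doses in the plural. A reader would take it that each dose has at most a 16% chance of missing its claim. If the figure is really that of one comparison taken alone, it overstates the prospects of two of the three doses.

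**Working it through.** **Inputs.** All come from SAP section 7: 15% on placebo, 45% on every PPC-06 dose and for both endpoints, two-sided 0.05, uncorrected chi-squared, 50 completers per arm. One placebo arm serves all three comparisons. The endpoint correlation is not given, so I take the range from independent to identical endpoints.

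**Step 1: reproduce the 84%.** Pooled normal approximation, one dose, one endpoint:

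- Null standard error: sqrt(2 × 0.30 × 0.70 / 50) = 0.09165.
- Alternative standard error: sqrt((0.15 × 0.85 + 0.45 × 0.55) / 50) = 0.08660.
- Power: Φ((0.30 − 1.96 × 0.09165) / 0.08660) = Φ(1.390) = 0.9177.
- Both endpoints, independent: 0.9177² = 0.842.

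At 100 per arm the same formula gives 99.5%, so the 84% rests on 50 completers. No step of the sequence enters it.

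**Step 2: power under the sequence.** Let g(x) be the probability that one dose beats placebo significantly on one endpoint when the placebo arm has x responders, summed over Binomial(50, 0.45). With x distributed as Binomial(50, 0.15), the probability that the first k doses all succeed on one endpoint is E[g(x)^k]. Conditioning on x accounts for the shared placebo arm. Power at step k is E[g^k] for identical endpoints and its square for independent ones. The normal-approximation version integrates over the placebo estimate in the same way.

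| Method, 50 per arm | Endpoints | 600 mg BID | 400 mg BID | 400 mg QD |
|---|---|---|---|---|
| Exact | independent | 85.0% | 75.1% | 67.9% |
| Exact | identical | 92.2% | 86.7% | 82.4% |
| Normal approximation | independent | 84.2% | 72.7% | 63.9% |
| Normal approximation | identical | 91.8% | 85.3% | 80.0% |

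**Step 3: correlations in between.** Independence is unlikely. Protocol section 7.3.1 says "The PASI is a measure of the average redness, thickness, and scaliness of the lesions", the IGA definitions grade the same three signs, and the same rater is to score both. Simulation with a bivariate-normal latent model, 400,000 trials per row:

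| Latent correlation | 600 mg BID | 400 mg BID | 400 mg QD |
|---|---|---|---|
| 0.5 | 85.9% | 76.7% | 69.9% |
| 0.8 | 87.1% | 78.5% | 72.2% |
| 0.95 | 88.5% | 80.9% | 75.2% |
| 0.995 | 90.2% | 83.6% | 78.5% |
| 0.999 | 91.0% | 84.7% | 80.0% |

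The same simulation at correlations 0 and 1 agrees with the exact values within 0.1 point. 400 mg BID crosses 84% only between latent 0.995 and 0.999, which is a phi coefficient of about 0.93 to 0.97 between the two responses.

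**Step 4: dependence on n.** Exact, independent endpoints:

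- 400 mg BID: 83.6% at 57 per arm and 84.6% at 58.
- 400 mg QD: 83.3% at 62 and 84.5% at 63.
- At 75 per arm the three doses have 97.1 / 94.6 / 92.5%; at 100, 99.5 / 99.1 / 98.7%.

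Exact, identical endpoints: 400 mg QD has 83.5% at 51 and 84.6% at 52.

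Normal approximation, independent endpoints: 400 mg BID passes 84% at 60 (84.8%) and 400 mg QD at 65 (84.5%).

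**The case against.** The strongest reply is that nothing is miscalculated. The paragraph opens by speaking of each dose group against placebo, and Protocol section 8.7.1 says that each dose is compared separately, so the 84% can be read as power per comparison, and as such it is right. That reading is available. But the text never says that the sequence is left out, and the figure directly follows the sequential rule and is attached to the doses in the plural.

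Second, completers are not the planned analysis set: "The primary efficacy analyses will be based on the FAS population using MI". Subjects who drop out contribute their earlier visits, so the effective number may exceed 50, and 8 to 13 more per arm would restore 84% for the lower doses even with independent endpoints. This stands. The documents do not give the effective number, so the power of the planned analysis is unknown. It limits the finding to the basis on which the plan itself quotes its figure.

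Third, the results depend on equal response rates at all doses. With rates of 55 / 50 / 45% from highest to lowest dose (an illustrative assumption), exact power at 50 per arm with independent endpoints is 98.5 / 93.6 / 81.3%, and 400 mg BID has no shortfall. Rates below 45% at the lower doses would widen it. The common 45% is the plan's own input.

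Finally, this is a Phase 2 trial, and the shell for Table 14.2.1.1.1 gives an odds ratio, confidence interval and p-value for every dose whatever happens higher up. True: a lower dose that is blocked loses confirmatory status, not its estimate. That bears on how serious the point is, not on whether the figure is right.

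**Conclusion.** The concern holds. As a statement about the planned procedure, a minimum of 84% is right for 600 mg BID only. For 400 mg QD it fails over the whole range from independent to identical endpoints, by 1.6 points at best (84 − 82.4) and 16.1 at worst (84 − 67.9), exact method. For 400 mg BID it fails by up to 8.9 points (84 − 75.1) and is met only when the two responses nearly coincide. With independent endpoints, the procedure has a 32.1% chance (100 − 67.9) of no confirmatory claim for 400 mg QD even if every design assumption is true.

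This rests on 50 informative subjects per arm, 15% against 45% at every dose, a shared placebo arm and an unadjusted chi-squared test. No estimate, p-value or error rate is affected. The sample size statement should be corrected because it credits two doses with power that the stated basis does not give them.

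**What to change.** In SAP section 7 and Protocol section 8.2:

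1. Label the 84% as power for one dose against placebo on both endpoints, before gatekeeping.
2. Add power by dose under the fixed sequence as a range from independent to identical endpoints, using one method throughout. Either take the exact method (85.0% per comparison) or keep the normal approximation (84.2% per comparison), with the matching rows of the first table above.
3. State that all doses are assumed to respond at 45% and that the figures refer to 50 completers per arm.
4. Say that the imputed FAS analysis may have a larger effective number, and give the thresholds for 84% by the same method. With independent endpoints, for 400 mg BID and 400 mg QD, these are 58 and 63 per arm (exact) or 60 and 65 (normal approximation).

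The cost is wording. Enrolment, alpha, testing order and analysis stay as they are. The sponsor would be publishing less favourable figures for the two lower doses, and the headline 84% becomes 85.0% if the exact method is chosen.

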## 8. ANALYSIS POPULATIONS

The following analysis sets/populations will be used in this trial:

- Safety population: include all subjects who receive at least one dose of IP. The safety population is the population used for all safety analyses.
- Full analysis set (FAS) – All randomized subjects who receive at least one dose of investigational product and have at least one post dose efficacy assessment. The FAS population will be the primary population for the efficacy analyses
- Per Protocol (PP) population: include subjects in the FAS population who complete the study without any major protocol violations that are considered likely to affect the efficacy analysis outcomes of the study. Major protocol violations will include but not be restricted to the following:
  - Failure to meet the inclusion/exclusion criteria that are considered likely to affect the efficacy analysis outcomes of the study
  - Randomization error

- Usage of any prohibited concomitant medications or procedures
- Failure to have Week 24 assessment within the allowable window for either of the co-primary endpoints
- Failure to be compliant with treatment regimen

Additional criteria may be added to determine PP population. The composition of the PP population will be determined and documented in blind reviews of the database conducted prior to unblinding the study database. Subjects who used rescue medications or who discontinued due to unsatisfactory therapeutic effect will be included in the PP population. These subjects will be considered as treatment failures (i.e., non-responder for both PASI-75 and IGA) for all time points after the initiation of rescue medications or subject discontinuation.

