	
The EOS Safety Follow-up Period will consist of 1 visit 1-week (\pm 3 days) following the Week 24 Visit or the ETV. In the event that the Week 24 Visit or the ETV occurs > 1 week following the last dose of the study drug, the EOS Safety Follow-up Visit may not be required. The ETV and/or EOS Safety Follow-Up Visit are not expected to be completed for subjects who withdraw full consent or are lost to follow up.
 
If necessary, the Investigator may decide to extend the follow-up visits beyond 1 week to monitor recovery of safety parameters (e.g., lymphopenia).

Planned Sample Size:	Approximately 400 subjects (~100 subjects per treatment arm)

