## 9. HANDLING OF MISSING DATA

All imputations specified in this section will be performed for the Double-Blind Treatment and titration Period only; the Post-treatment Follow-Up Period data will be analyzed as observed.

For the analyses of the co-primary endpoints (PASI-75 and IGA), multiple imputation (MI) will be the primary imputation method. The modified non-responder imputation (m-NRI) and last observation carried (LOCF) method will be used as sensitivity analyses.

Details of the imputation methods are as following:

- **MI:** Missing data will be imputed using multiple imputations, a simulation-based approach where missing values are replaced by multiple Bayesian draws from the conditional distribution of missing data given the observed data and covariates, creating multiple completed data sets. These completed datasets can then be analyzed using standard analysis methods. MI will be implemented for all subjects with missing data, included those who used rescue medications or discontinued due to unsatisfactory therapeutic effect.

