### Multiple Imputation procedures for missing PASI scores:

Intermittent missing values of PASI scores will be imputed separately for each treatment group using the Markov Chain Monte Carlo (MCMC) method, generating 50 copies of the imputed dataset with monotonic missing pattern. For each of the 50 datasets, missing values at scheduled visits (Weeks 4, 8, 12, 16, 20 and 24) will be imputed using a linear regression model. The imputations will include the following variables: baseline BMI, baseline PASI score, and PASI scores at the previous scheduled visits. SAS Proc MI will be used. Imputed PASI-75 response (Yes/No) will be derived for each imputed dataset.

Example SAS code is as follows:

```
PROC MI DATA = PASI1 OUT = PASI2 SEED = 132138 NIMPUTE = 50 NOPRINT;  
BY TRT01PN;
```

```
MCMC IMPUTE = MONOTONE;  
VAR BASEBMI BASEPASI _3 _4 _5 _6 _7 _8;  
RUN;  
  
PROC MI DATA = PASI2 OUT= PASI3 SEED = 132138 NIMPUTE = 1 NOPRINT;  
BY TRT01PN _IMPUTATION_;  
MONOTONE REGRESSION;  
VAR BASEBMI BASEPASI _3 _4 _5 _6 _7 _8;  
RUN;
```

Multiple Imputation procedures for missing IGA scores:

The imputation of post-baseline IGA scores will be performed following a similar approach as described for PASI scores. Intermittent missing IGA scores will be imputed separately for each treatment group using the Markov Chain Monte Carlo (MCMC) method where 50 copies of the dataset with monotonic missing pattern will be generated. For each of the 50 datasets, missing values at scheduled visits (Weeks 4, 8, 12, 16, 20 and 24) will be imputed using a logistic regression model including baseline BMI, baseline IGA score, and IGA scores at the previous scheduled visits. SAS Proc MI using the logistic regression method for monotone data will be used for the imputation. IGA Treatment Success status (Yes/No) will then be derived for each imputed dataset.

Example SAS code is as follows:

```
PROC MI DATA = IGA1 OUT = IGA2 SEED = 132138 NIMPUTE = 50 NOPRINT;  
BY TRT01PN;  
MCMC IMPUTE = MONOTONE;  
VAR BASEBMI _3 _4 _5 _6 _7 _8;  
RUN;  
  
PROC MI DATA = IGA2 OUT= IGA3 SEED = 132138 NIMPUTE = 1 NOPRINT;  
BY TRT01PN _IMPUTATION_;  
MONOTONE LOGISTIC;  
VAR BASEBMI _3 _4 _5 _6 _7 _8;  
RUN;
```

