### 11.4 Analysis Visit Window

Efficacy and safety endpoints will be analyzed according to their windowed visits defined by actual study day. If more than one visit occurs within a single visit window, then the analysis will take the one closest to the target day. If the 2 visits are equidistant from the target day, the later visit will be used. A later visit within the window will be used for LOCF.

The following analysis visit windows will apply:

Visit	Week	Target Day	Efficacy Assessment Window	Safety Assessment Window
2	Baseline	0	On or prior to date of first dose	On or prior to date of first dose
3	4	28	Post-dose – Day 42	Post-dose – Day 42
4	8	56	Day 43 – Day 70	Day 43 – Day 70
5	12	84	Day 71 – Day 98	Day 71 – Day 98
6	16	112	Day 99 – Day 126	Day 99 – Day 126
7	20	140	Day 127 – Day 154	Day 127 – Day 154
8	24	168	≥Day 155	≥Day 155
9 (Follow-Up)	25	LD+7	> LD+15	> LD+15

LD = Last dose date

Visits 3 through 8 are on-treatment visits. Therefore, only on-drug assessments or assessments performed within 15 days post last dose are to be analyzed within those windows, according to their actual study day. Visit 9 is an off-treatment visit, which will be analyzed according to their number of days after last dose, regardless of the actual study day. For example, a subject who has Visit 4 on Day 56, then discontinues with last dose on Day 84 and returns for Early Termination on Day 100 will have no data within the Visit 6 window. The Early Termination visit must be analyzed as Visit 9. For this subject, data for Visits 5, 6, 7, and 8 would be carried forward from Visit 4 in an LOCF analysis. If the last dose date is unknown, then all visits will be analyzed as on-treatment based on actual study day (i.e., no Visit 9 will be identified for the subject).

Subjects who permanently discontinue the study drug for any reason or who withdraw from the study prematurely prior to the end of the Double-Blind Treatment Period should undergo the ETV followed by the EOS Safety Follow-up Period Visit. In the event that the ETV or Week 24 Visit occurs > 1 week following the last dose of the study drug, the EOS Safety Follow-up Visit may not be required. If necessary, the Investigator may decide to extend the EOS Safety Follow-up Visits beyond 1 week to monitor recovery of safety parameters (eg, lymphopenia).

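### The full analysis set leaves out dosed subjects with no post-dose efficacy assessment, mainly early dropouts who withdraw consent or are lost, and no planned efficacy analysis includes them

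*SAP*

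**What the plan says.** SAP 8 gives the FAS definition as "All randomized subjects who receive at least one dose of investigational product and have at least one post dose efficacy assessment", and Protocol 8.3 has the same rule. SAP 12.8.1 makes it the primary set: "The primary efficacy analyses will be based on the FAS population using MI".

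The first regular post-baseline PASI and IGA assessment is at Week 4, Day 28 ± 3 (Protocol Table 1-1). Before then a score can come from an ETV: "The Early Termination Visit (ETV) will be scheduled if the study drug is permanently discontinued for any reason" (SAP 3, with unresolved GI intolerance as an example). Protocol 7.2.4 has PASI, BSA and IGA assessed there, and Protocol 7.2.5 has them assessed again at safety follow-up. But the Protocol Synopsis says that the ETV and the follow-up visit "are not expected to be completed for subjects who withdraw full consent or are lost to follow up".

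SAP 11.4 sets the Week 4 window from first dose to Day 42 and adds that, for Visits 3 to 8, "only on-drug assessments or assessments performed within 15 days post last dose are to be analyzed within those windows". Later assessments are analysed as Visit 9.

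For PASI, SAP 9 states: "The imputations will include the following variables: baseline BMI, baseline PASI score, and PASI scores at the previous scheduled visits".

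**The concern.** FAS membership depends on something that happens after randomisation. Subjects receive active drug from Week 1 of titration (Protocol Table 6-1), and the protocol names diarrhoea, nausea, abdominal pain and flushing as the common adverse events of PPC-06 (Protocol 7.5.1.4). Some subjects with these events may simply stop coming. If that happens more often on active drug, and if those subjects would not have responded, removing them raises the active response rate more than the placebo rate in both co-primary comparisons. The plan expects 50% dropout, so early loss is not a remote possibility.

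The exclusion is also unnecessary. The PASI imputation model already contains baseline predictors, so a subject needs no post-baseline score to be imputed.

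**Working it through.** **1. The plan's own figure.** The rates used below come from SAP 7: "assuming a 15% response rate for the placebo group and 45% for PPC-06 at Week 24". With 50 completers per arm and a pooled-variance chi-squared test at two-sided 0.05:

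- Standard error under the null: √(2 × 0.30 × 0.70 / 50) = 0.0917.
- Standard error under the alternative: √((0.15 × 0.85 + 0.45 × 0.55) / 50) = 0.0866.
- z = (0.30 − 1.96 × 0.0917) / 0.0866 = 1.39, so power is 91.8% per endpoint.
- Both endpoints, treated as independent: 0.918² = 84.2%.

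This reproduces the stated 84%, and nothing here disputes it.

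**2. Who leaves the FAS.**

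| Dosed subject who stops before Week 4 | Post-dose PASI/IGA | In FAS |
|---|---|---|
| Attends ETV within 15 days of last dose | Yes, analysed as Week 4 if by Day 42 | Yes |
| Attends ETV more than 15 days after last dose | Yes, analysed as Visit 9 | Yes (the definition sets no window) |
| Withdraws full consent or is lost, no visit | None | No |

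The second row shows that the plan already needs imputation from baseline alone. Protocol 4.1 sends subjects off drug for more than two consecutive weeks to an ETV, so late ETVs will occur. Such a subject is in the FAS with no on-treatment score.

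**3. Whether another planned analysis picks them up.** The imputation summary in SAP 9 runs MI, m-NRI, LOCF and OC on the FAS, and the per-protocol set is a subset of the FAS. So none does.

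**4. Size.** The documents give no count, so everything in this step is assumption.

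- Constant hazard with 50% dropout over 24 weeks gives 1 − exp(−ln 2 × 4/24) = 10.9% leaving before Week 4.
- If 25% to 75% of them have no assessment at all: 0.25 × 10.9 = 2.7 and 0.75 × 10.9 = 8.2, or about 3 to 8 per 100.
- Take 45% and 15% as the FAS rates and treat all excluded subjects as non-responders. Then all-dosed rate = FAS rate × (1 − share excluded), and OR = [pA/(1 − pA)] / [pP/(1 − pP)].

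| Excluded per 100, active / placebo | Active | Placebo | Difference | OR |
|---|---|---|---|---|
| 0 / 0 | 45.0% | 15.0% | 30.0 points | 4.64 |
| 3 / 3 | 0.45 × 0.97 = 43.65% | 0.15 × 0.97 = 14.55% | 29.1 points | 4.55 |
| 8 / 3 | 0.45 × 0.92 = 41.4% | 14.55% | 26.9 points | 4.15 |
| 8 / 8 | 41.4% | 0.15 × 0.92 = 13.8% | 27.6 points | 4.41 |

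**5. What MI would do with them.** Imputation is run separately by treatment group. With only baseline predictors, these subjects would be drawn at roughly their own arm's rate, so the difference would stay near 30 points. This is reasoning, not a simulation.

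**The case against.** The strongest objection is that the plan largely closes this gap. Any permanent stop of study drug triggers an ETV with PASI and IGA, and an early ETV usually counts as Week 4 data. A reader might infer from the FAS wording that early intolerance dropouts as a class leave the primary analysis. The documents do not support that: only subjects with no post-dose assessment at all are removed. This part of the objection stands and limits the point to that group.

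The documents also do not show imbalance. They give no attrition by arm and no reasons for missed ETVs, and SAP 7 applies 50% dropout to every arm. A difference between arms is plausible from the adverse-event profile, no more. A larger shift can be constructed: 12 active and 4 placebo exclusions would give 0.45 × 0.88 = 39.6% against 0.15 × 0.96 = 14.4%, or 25.2 points. But 12 is more than the roughly 11 per 100 who would leave before Week 4 for any reason under the constant hazard.

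Third, adding these subjects to within-arm MI moves the estimate little. That is correct. Redefining the set restores the randomised comparison but does not treat early loss as failure. The present m-NRI does not do so either: it fails only rescue use and lack-of-efficacy discontinuation and leaves other missing data missing.

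Finally, SAP 9 says "MI will be implemented for all subjects with missing data", which could be read as already covering this group. It does not, because the primary analysis applies MI within the FAS. Table 14.1.1 will show FAS counts by arm but lists no reasons for FAS exclusion.

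**Conclusion.** The point holds in limited form. The plan removes dosed subjects with no post-dose efficacy assessment from every efficacy analysis, by a condition that arises after randomisation and that no planned sensitivity analysis can undo. Under the assumptions above (3 to 8 active and 3 placebo excluded per 100, all non-responders), the FAS would overstate the difference by about 0.9 to 3.1 points (30 − 29.1 and 30 − 26.9). If the excluded subjects would have responded at their arm's rate, the shift is nil. The true number cannot be derived from the documents. The plan should be changed because the exclusion is avoidable at little cost, not because a large bias has been shown.

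**What to change.** 1. In SAP 8 and Protocol 8.3, define the primary efficacy set as all randomised subjects who received at least one dose, analysed by randomised arm.
2. Include subjects with no post-baseline score in the planned MI. Add baseline IGA to the example IGA code: the text names it as a predictor, but the code lists only baseline BMI before the visit scores, so as written these subjects' IGA would be imputed from BMI alone.
3. Add a sensitivity analysis on this set that counts every subject with a missing Week 24 result after discontinuation as a non-responder, including those with no post-baseline score. It must cover all such dropouts. Otherwise an early dropout without an ETV would count as a failure while one with an ETV stayed missing.

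The cost is wording and minor programming, with no new data. Response rates in the primary analysis may be slightly lower. The sensitivity analysis will lower them further because it covers all dropouts. If 45% and 15% are completer rates and the full 50% dropout has no Week 24 result, it would give 0.45 × 0.5 = 22.5% against 0.15 × 0.5 = 7.5%. It should therefore be labelled in advance as a conservative check.
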